### 9.7 Gender and Minority Accrual Estimates

The gender and minority distribution of the study population is expected to be:

Racial category	Ethnicity				Total
	Not Hispanic or Latino		Hispanic or Latino		
	Female	Male	Female	Male	
American Indian/Alaska Native	0	0	0	0	0
Asian	1	4	0	0	5
Black or African American	14	6	0	0	20
White	38	27	8	16	89
More than one race	0	0	0	0	0
Total	53	37	8	16	114

This distribution was derived from the demographic data for patients enrolled on recent COG Phase 2 trials ADVL0821 and ADVL0921 with diagnoses among the primary disease groups.

### 9.8 Analysis of the Pharmacokinetic Parameters

A descriptive analysis of pharmacokinetic (PK) parameters of IMG901 will be performed to define systemic exposure, drug clearance, and other pharmacokinetic parameters. The PK parameters will be summarized with simple summary statistics, including means, medians, ranges, and standard deviations (if numbers and distribution permit).

### 9.9 Analysis of Biological and Correlative Endpoints

#### CD56 Expression

The association between CD56+ expression and response will be evaluated using the exact conditional test of proportions (Fisher's Exact Test).

#### Pharmacokinetics

A descriptive analysis of pharmacokinetic (PK) parameters of IMG901 will be performed to define systemic exposure, drug clearance, and other pharmacokinetic parameters. The PK parameters will be summarized with simple summary statistics, including means, medians, ranges, and standard deviations (if numbers and distribution permit).

All these analyses will be descriptive and exploratory and hypotheses generating in nature.

## 10.0 EVALUATION CRITERIA

### 10.1 Common Terminology Criteria for Adverse Events (CTCAE)

This study will utilize the CTCAE of the National Cancer Institute (NCI) for toxicity and performance reporting. The descriptions and grading scales found in the revised CTCAE version 4.0 will be utilized for reporting. All appropriate treatment areas should have access to a copy of the CTCAE version 4.0, which can be downloaded from the CTEP web site ([http://ctep.cancer.gov/protocolDevelopment/electronic\\_applications/ctc.htm](http://ctep.cancer.gov/protocolDevelopment/electronic_applications/ctc.htm)). Additionally, toxicities are to be reported on the appropriate case report forms.

### 10.2 Response Criteria

As outlined, patients will be assigned to one of the following categories for assessment of response: a) solid tumor and measurable disease ([Section 10.3](#)); b) neuroblastoma with MIBG positive lesions ([Section 10.4](#)); c) neuroblastoma with bone marrow involvement ([Section 10.5](#)); Note: Neuroblastoma patients who do not have MIBG positive lesions or bone marrow involvement should be assessed for response as solid tumor patients with measurable or evaluable disease.

### 10.3 Response Criteria for Patients with Solid Tumors (non-CNS)

Response and progression will be evaluated in this study using the revised Response Evaluation Criteria in Solid Tumors (RECIST) guideline (version 1.1.) Key points are that 5 target lesions are identified and that changes in the *largest* diameter (unidimensional measurement) of the tumor lesions are used in the RECIST v 1.1 criteria.

#### 10.3.1 Measurable Disease

The presence of at least one lesion that can be accurately measured in at least one dimension with the longest diameter at least 10 mm (CT scan slice thickness no greater than 5 mm). The investigator will identify up to 5 measurable lesions to be followed for response. Previously irradiated lesions must demonstrate clear evidence of progression to be considered measurable.

Serial measurements of lesions are to be done with appropriate imaging modalities, e.g., CT or MRI. Bone scans cannot be used to measure lesions. The same method of assessment is to be used to characterize each identified and reported lesion at baseline and during follow-up.

#### 10.3.2 Quantification of Disease Burden

The sum of the longest diameter (LD) for all target lesions will be calculated and reported as the disease measurement.

#### 10.3.3 End-of-Cycle Response

Note: Please also see Table 1 in [Section 10.6](#).

##### a) Complete Response (CR)

Disappearance of all target and non-target lesions. Normalization of urinary catecholamines (for patients with neuroblastoma), immunocytologic findings, or other tumor markers if abnormal or elevated at study enrollment.

b) Partial Response (PR)

At least a 30% decrease in the disease measurement, taking as reference the disease measurement done to confirm measurable disease at study enrollment. No new lesions or progression of any non-target measurable lesion.

c) Stable Disease (SD)

Neither sufficient shrinkage to qualify for PR nor sufficient increase to qualify for PD taking as reference the smallest disease measurement since the treatment started.

d) Progressive Disease (PD)

At least a 20% increase in the sum of the disease measurements for measurable lesions, taking as reference the smallest disease measurement recorded since the start of treatment, or the appearance of one or more new lesions.

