#### 3.1.5 Timing

Patients must be enrolled before treatment begins. The date protocol therapy is projected to start must be no later than 7 business days after the date of study enrollment. **Patients who are started on protocol therapy prior to study enrollment will be considered ineligible and will not be able to receive further protocol therapy.**

See [Section 3.2](#) for timing requirements for eligibility studies. See [Section 3.1.7](#) for timing requirements for baseline studies to be obtained prior to start of therapy.

Institutions are advised to plan ahead to ensure adequate and timely delivery of the investigational agent (see [Section 6.1.5](#) for details).

**Note: Repeat laboratory and imaging studies may be required if enrollment and start of therapy do not occur on the same day.**

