3.1.7 Requirements to Initiate Protocol Therapy

3.1.7.1 Laboratory Studies: If more than 7 calendar days elapse between the date laboratory studies to determine eligibility were obtained ([Section 3.2.5](#)) and the start date of treatment, then the following studies must be repeated prior to initiating protocol therapy: CBC with differential, bilirubin, ALT (SGPT) and serum creatinine. If any of these repeat laboratory studies are outside the parameters required for eligibility (labs may again be repeated within 48-72 hours), then the patient is off protocol therapy.

3.1.7.2 Imaging Studies: Imaging studies must be performed within 14 calendar days of initiating protocol therapy. If more than 14 calendar days have elapsed between the date imaging studies to determine eligibility were obtained ([Section 3.2.3](#)) and the start date of treatment, then repeat imaging studies must be obtained prior to initiating protocol therapy.

3.1.7.3 Bone Marrow Evaluations: For patients with known or clinically suspected bone marrow involvement, BMA and/or biopsy must be performed within 14 calendar days of initiating protocol therapy. If more than 14 calendar days have elapsed between the date bone marrow evaluation to determine eligibility was obtained ([Section 3.2.3](#)) and the start date of treatment, then repeat BMA and/or biopsy must be obtained prior to initiating protocol therapy.

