### 3.2 Eligibility: Inclusion Criteria

**Important note: The inclusion criteria listed below are interpreted literally and cannot be waived. All clinical and laboratory data required for determining eligibility of a patient enrolled on this trial must be available in the patient's medical/research record. These source documents must be available for verification at the time of audit.**

All clinical and laboratory studies to determine eligibility must be performed within 7 days prior to enrollment. Imaging studies must be performed within 14 days prior to study enrollment.

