10.3.4 Overall Best Response Assessment

Each patient will be classified according to their “best response” for the purposes of analysis of treatment effect. Best response is determined from the sequence of the objective statuses described in [Section 10.6 \(Tables 1-3\)](#).

10.4 **Response Criteria for Neuroblastoma Patients with I-MIBG Positive Lesions**10.4.1 MIBG Positive Lesions

Patients who have a positive MIBG scan at the start of therapy will be evaluable for MIBG response. The use of I for MIBG imaging is recommended for all scans. If this isotope is unavailable at the treating institution, the use of the same radioisotope for all MIBG scans for an individual patient is strongly encouraged.

10.4.2 The following criteria will be used to report MIBG response by the treating institution:

- **Complete Response:** Complete resolution of all MIBG positive lesions
- **Partial Response:** Resolution of at least one MIBG positive lesion, with persistence of other MIBG positive lesions.
- **Stable Disease:** No change in MIBG scan in number of positive lesions (includes patients who have same number of positive lesions but decreased density).
- **Progressive Disease:** Development of new MIBG positive lesions.

[figure not shown]
10.4.3 The response of MIBG lesions will be assessed on central review using the Curie scale as outlined below. Central review responses will be used to assess efficacy for study endpoint. See [Section 7.3](#) for details on transferring images to the Imaging Research Center.

NOTE: This scoring is NOT required to be done by the treating institution for end of course response assessments.

The body is divided into 9 anatomic sectors for osteomedullary lesions, with a 10th general sector allocated for any extra-osseous lesion visible on MIBG scan. In each region, the lesions are scored as follows. The **absolute extension score** is graded as:

- 0 = no site per segment,
- 1 = 1 site per segment,
- 2 = more than one site per segment,
- 3 = massive involvement (>50% of the segment).

The **absolute score** is obtained by adding the score of all the segments. See diagram of sectors below:

The **relative score** is calculated by dividing the absolute score at each time point by the corresponding pre-treatment absolute score. The relative score of each patient is calculated at each response assessment compared to baseline and classified as below:

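### Partial response is measured from the enrolment scan even when the protocol requires a newer scan before the first dose, so pre-dose change in either direction is counted as drug effect

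*Combined protocol and SAP*

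**What the plan says.** Four provisions of the combined protocol and SAP bear on the PR reference.

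- **Eligibility imaging (Section 3.2).** "Imaging studies must be performed within 14 days prior to study enrollment".
- **Start of therapy (Section 3.1.5).** The projected start "must be no later than 7 business days after the date of study enrollment". The section points to 3.1.7 for the timing of the baseline studies due before therapy, and warns that imaging may have to be repeated if enrolment and first dose fall on different days.
- **Repeat imaging (Section 3.1.7.2).** "If more than 14 calendar days have elapsed between the date imaging studies to determine eligibility were obtained" and the first day of treatment, "then repeat imaging studies must be obtained prior to initiating protocol therapy".
- **Response (Section 10.3.3).** PR is "At least a 30% decrease in the disease measurement", "taking as reference the disease measurement done to confirm measurable disease at study enrollment". Progression in the same section is judged "taking as reference the smallest disease measurement recorded since the start of treatment".

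Section 10.3.1 speaks of assessing lesions at baseline and in follow-up but does not say which scan is the baseline. For MIBG disease, Section 10.4.3 forms the relative score by "dividing the absolute score at each time point by the corresponding pre-treatment absolute score".

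Section 9.3 makes objective response the primary endpoint, with 16 evaluable patients per stratum and a written threshold of at least 4 centrally confirmed responses.

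**The concern.** Section 3.1.7.2 distinguishes two scans: the one that established eligibility, and a later one that is compulsory when the first is too old. The PR definition names the first. For a rescanned patient, the plan therefore collects a more recent measurement and then, as written, does not use it for the primary endpoint.

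The measured change then covers an untreated interval as well as the treated one. If the tumour grew in that interval, the drug has to make up the growth before any shrinkage counts. If the tumour shrank, or simply measured smaller on the second scan, part of the required 30% is credited before any drug is given. Either way the classification no longer describes change on treatment.

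The inconsistent terms also allow a site and the central reviewer to choose different references for the same patient. Response decides whether a small stratum is declared active, so the reference should not be left to interpretation.

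**Working it through.** The plan gives no figure on this point to reproduce. The check asks whether a forced rescan can arise within the plan's own windows, and what it does to the PR criterion.

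**Inputs from the plan.** Eligibility scan up to 14 days before enrolment (3.2). Projected start up to 7 business days after enrolment (3.1.5). Rescan if more than 14 calendar days separate eligibility scan and first dose (3.1.7.2). PR threshold 30% (10.3.3 b). 16 evaluable patients per stratum and at least 4 responses (9.3).

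**Assumed input.** The relative change *g* in the sum of diameters between the two pre-dose scans. The plan gives no value, so a range is shown.

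**Step 1: can it happen without a deviation?** Seven business days are 9 calendar days after a Monday to Wednesday enrolment and 11 after a Thursday or Friday enrolment, ignoring holidays. The longest planned gap is 14 + 9 = 23 to 14 + 11 = 25 days, well beyond the 14-day trigger. Neither window has to be used in full: a scan 10 days old at enrolment with a first dose 5 days later gives 10 + 5 = 15 days and forces a rescan. Conversely, a scan no more than 14 − 11 = 3 days old at enrolment cannot trigger one if the start keeps to 3.1.5.

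**Step 2: effect on PR.** Let *E* be the sum at the enrolment scan, *B* = *E*(1 + *g*) the sum at the repeat scan, and *F* the sum at follow-up. As written, PR needs *F* ≤ 0.70*E*.

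- Fall from *B* needed for PR: 1 − 0.70/(1 + *g*).
- Fall recorded when the true fall from *B* is exactly 30%: 1 − 0.70(1 + *g*).

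| Pre-dose change *g* (assumed) | Fall from repeat scan needed for PR | True 30% fall is recorded as |
|---|---|---|
| −10% | 22.2% | 37.0% |
| 0 | 30.0% | 30.0% |
| +5% | 33.3% | 26.5% |
| +10% | 36.4% | 23.0% |
| +20% | 41.7% | 16.0% |
| +30% | 46.2% | 9.0% |

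For example, at *g* = +10%: 1 − 0.70/1.10 = 36.4%, and 1 − 0.70 × 1.10 = 23.0%. At *g* = −10%: 1 − 0.70/0.90 = 22.2%.

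**Step 3: who is reclassified.** Only rescanned patients whose best fall lies between the two thresholds. With 10% growth these are falls of 30% up to 36.4% from the repeat scan, which lose PR. With 10% shrinkage they are falls of 22.2% up to 30%, which gain it.

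**Step 4: weight of one patient.** 1/16 = 6.25 percentage points of the stratum response rate. In a stratum sitting at the written threshold, one patient moves the count from 4 to 3 or from 3 to 4 and changes the decision.

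**The case against.** The best defence is that the plan already treats the later scan as baseline. Section 3.1.5 calls the Section 3.1.7 studies baseline studies, Section 10.3.1 has lesions assessed at baseline, and Section 8.1 g) refers to repeat eligibility studies. A site could reasonably take the repeat scan as the one confirming measurable disease. This stands as evidence that the text is inconsistent. It does not displace the explicit tie to study enrolment in the PR definition, and no section says that the repeat scan takes over.

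The second defence is size. Only patients whose CT or MRI is more than 14 days old at the first dose are touched, and among them only those near the 30% threshold. Complete response requires disappearance of disease and does not depend on the reference size. Section 9.5 allows six cycles for best response, so a deepening response can still qualify. All of this stands, and the affected group may be very small.

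Two stronger readings are tempting, and the documents support neither.

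- **The rule lowers the response rate and costs power.** The bias can run either way, as the −10% row shows, and the plan gives neither the share rescanned nor any growth rate. A power figure would rest wholly on an assumed fraction of lost responders.
- **The CT/MRI and MIBG systems use different baselines.** An eligibility MIBG scan is also a pre-treatment scan. Section 10.4.3 does not say which pre-treatment scan it means, so a conflict is not shown; the term needs the same clarification.

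**Conclusion.** The concern holds as a defect in the definition of the primary endpoint. As written, Section 10.3.3 b) refers PR to a scan that Section 3.1.7.2 may have treated as too old to start therapy on, and the plan's terms for baseline do not agree with one another. The situation can arise within the permitted windows, with planned gaps of up to 23 to 25 days.

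For a rescanned patient the PR criterion shifts with the pre-dose change: from a 30% fall to 36.4% after an assumed 10% growth, or to 22.2% after a 10% shrinkage. The formulas are exact; the growth values are assumptions. The number of patients affected, the net direction of the bias and any effect on power cannot be derived from the documents. What can be said is that each reclassified patient is 1 of 16 in the stratum. This is a correction worth making, not evidence that the trial's conclusion would change.

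**What to change.** In Section 10.3.3 b), make the PR reference *the last disease measurement obtained before the first dose of IMGN901 (the repeat scan where 3.1.7.2 requires one)*. Then, in the same place or in Section 10.3.1:

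- state that this baseline is also the starting value for the smallest-measurement reference used for progression, since at the first evaluation there is no earlier on-treatment measurement to compare with;
- state that central review uses the same baseline;
- state that the pre-treatment score in Section 10.4.3 refers to the same time point.

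The repeat scan is already compulsory, so no procedure is added. The cost is a check of patients already enrolled (10 + 8 + 5 = 23 in the three primary strata before Amendment #1, Section 9.1.1, plus any since and any in the secondary strata) to find who was rescanned, re-derive their baseline sums, and align central review. Reporting how many were rescanned, and whether any classification changes, would show how much the choice mattered.

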#### 3.2.3 Disease Status

- 3.2.3.1 Patients must have radiographically measurable disease (with the exception of those with neuroblastoma, see [Section 3.2.3.2](#)).

Measurable disease is defined as the presence of at least one lesion on MRI or CT scan that can be accurately measured with the longest diameter a minimum of 10 mm in at least one dimension (CT scan slice thickness no greater than 5 mm).

Note: The following do not qualify as measurable disease:

- malignant fluid collections (e.g., ascites, pleural effusions)
- bone marrow infiltration except that detected by MIBG scan for neuroblastoma, see [Section 3.2.3.2](#)
- lesions only detected by nuclear medicine studies (e.g., bone, gallium or PET scans) except as noted in [Section 3.2.3.2](#)
- elevated tumor markers in plasma or CSF
- previously radiated lesions that have not demonstrated clear progression post radiation
- leptomeningeal lesions that do not meet the measurements noted above.

3.2.3.2 Patients with **neuroblastoma** who do not have measurable disease but have MIBG-avid evaluable disease are eligible.

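### The PR definition in Section 10.3.3 b) lets only new lesions or a progressing measurable non-target lesion block a response, so clear worsening of a baseline effusion or of bone disease outside the MIBG rules does not prevent a PR

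*Combined protocol and SAP*

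**What the plan says.** Section 10.3.3 of the protocol defines the end-of-cycle categories for solid tumors.

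- **CR:** "Disappearance of all target and non-target lesions", with tumor markers normalized. Non-target disease counts whether or not it can be measured.
- **PR:** "At least a 30% decrease in the disease measurement" from baseline, plus "No new lesions or progression of any non-target measurable lesion".
- **PD:** "At least a 20% increase in the sum of the disease measurements for measurable lesions", "or the appearance of one or more new lesions".

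Section 3.2.3.1 lists what does not qualify as measurable. The list includes "malignant fluid collections (e.g., ascites, pleural effusions", marrow infiltration and lesions seen only on nuclear studies (both with an exception for MIBG in neuroblastoma), and "leptomeningeal lesions that do not meet the measurements noted above". Section 10.3.1 adds: "Bone scans cannot be used to measure lesions".

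Section 9.3 makes objective response by RECIST the primary endpoint, and Section 10.3 names version 1.1. Neither section writes out that guideline's rule for non-target disease. Section 9.4 points to Section 10.0 for the response criteria.

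**The concern.** The word *measurable* limits PR and PD but not CR. Existing disease that cannot be measured therefore has to vanish for a CR, yet its worsening neither blocks a PR nor makes PD under 10.3.3. A patient with lung nodules down 35% and a baseline malignant effusion that has clearly enlarged meets the written PR definition.

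Response is the primary endpoint in every stratum, and each stratum is decided on a few responses among 16 evaluable patients. One patient misclassified in this way can change a stratum's conclusion, and the error can only add responders.

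**Working it through.** **1. Does any other section close the gap?**

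| Baseline disease | Rule elsewhere | Does worsening block PR? |
|---|---|---|
| Malignant effusion or ascites | None found | No |
| Existing lesion on bone scan | 10.4.5: PD means new lesions only; otherwise neither CR nor PD. Table 2 allows overall PR with a bone scan that is not PD, and Table 3 does likewise | No |
| MIBG-avid disease, neuroblastoma | 10.4.3: PR needs a relative Curie score of 0.5 or less. Every PR row of Tables 2 and 3 needs MIBG CR or PR | Yes |
| Marrow, neuroblastoma | 10.5.1: a doubling, with at least 25% tumor, is PD. Tables 2 and 3 carry this to overall PD | Yes |
| Marrow, other strata | 3.2.5.1 b admits such patients; 10.5 is written for neuroblastoma | No rule found |
| Small leptomeningeal lesions | None, but 3.3.4 excludes active CNS metastases | No, but rare |

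The gap is clearest for effusions. It also exists for bone disease outside the MIBG rules.

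**2. Effect on best response.** Section 10.6, Table 1 scores PR followed by progression as progressive disease, and PR followed by PR as PR. If worsening of non-measurable disease at the second assessment is not called progression, the patient is a confirmed responder.

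**3. The plan's own operating characteristics.** Inputs from Section 9.3: n = 16, null rate 0.15, alternative 0.40, cutoff at least 4 responses, stated type I error 0.079 and power 0.833.

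Formula: P(X ≥ r) = 1 − Σ over k < r of C(16,k) p^k (1−p)^(16−k).

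At p = 0.15 the terms for k = 0 to 4 are 0.0743, 0.2097, 0.2775, 0.2285 and 0.1311.

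- P(X ≥ 4) = 1 − (0.0743 + 0.2097 + 0.2775 + 0.2285) = 0.210
- P(X ≥ 5) = 0.210 − 0.131 = 0.079

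At p = 0.40 the two cutoffs give 0.935 and 0.833. The stated 0.079 and 0.833 are therefore reproduced by a cutoff of 5, not by the written 4. That discrepancy is a separate matter, so both cutoffs are shown below.

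**4. Illustrative sensitivity.** Let q be the share of all patients who are not true responders but are scored PR through this gap. The documents give no value for q; 2% and 5% are assumptions. The counted rate is 0.15 + q.

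| q | Counted rate | Expected wrong PRs in 16 (16q) | P(X ≥ 4) | P(X ≥ 5) |
|---|---|---|---|---|
| 0% | 0.15 | 0 | 0.210 | 0.079 |
| 2% | 0.17 | 0.32 | 0.284 | 0.121 |
| 5% | 0.20 | 0.80 | 0.402 | 0.202 |

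At q = 5%, 0.05/0.20 = one in four counted responders would be wrong. At q = 2% the share is 0.02/0.17 = 12%.

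**The case against.** **RECIST is named.** Sections 9.3 and 10.3 set RECIST as the standard, and only centrally confirmed responses count. A central reader might apply a broader non-target rule than 10.3.3 states. This stands as a limit: the text is in tension with the guideline it cites, and one cannot say that such patients will be counted. It does not remove the problem. The protocol does not reproduce the guideline's rule, and nothing says which text prevails.

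**Confirmation is an obstacle.** A PR needs two consecutive assessments at least 3 weeks apart (10.6). Section 4.1.3 requires a patient to be stable, both clinically and on imaging, to continue. A patient with an obviously growing effusion may stop treatment. If other anti-cancer therapy then starts before confirmation, Section 9.5 makes the patient inevaluable. This lowers the frequency. It does not close the route, because 4.1.3 governs treatment and not classification, and Section 7.1 includes an end-of-therapy tumor evaluation.

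**Inferences that the documents do not support.**

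- A reader might infer that strata with bone and marrow disease are hit hardest. Neuroblastoma, for which the bone and marrow rules are mainly written, is largely protected by the MIBG and marrow rows.
- Leptomeningeal disease might look like a leading example. Section 3.3.4 makes it rare.
- A progressing measurable non-target lesion blocks PR but may not be PD if the sum is confined to targets (10.3.2). That is untidy, but the patient is a non-responder either way, so the response count does not change.
- The 0.40 or 0.20 at q = 5% might be read as an estimate of the error rate. It is one point on an assumed range.

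**Conclusion.** The point holds for the PR definition. As written, 10.3.3 b) does not let clear worsening of a baseline malignant effusion, or of bone disease outside the MIBG rules, prevent a PR. That is inconsistent with the CR definition and unreconciled with the guideline named in Sections 9.3 and 10.3. The direction of bias is upward.

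Its size is unknown. The illustration assumes a true rate of 15%, independent patients, and wrong PRs that come only from true non-responders. On those assumptions, 2% to 5% wrongly scored raises the chance of declaring activity from 0.21 to between 0.28 and 0.40 at a cutoff of 4, or from 0.08 to between 0.12 and 0.20 at a cutoff of 5. The finding rests on the literal text and not on any evidence that a patient has been misclassified.

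**What to change.** For response classification, replace the last sentence of 10.3.3 b) with: *No new lesions and no unequivocal progression of any non-target lesion, measurable or not.* Cross-refer it to 10.4.5 and to Tables 2 and 3 in 10.6, so that the bone scan columns are read the same way. Have central review apply it to every counted responder in all strata.

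Separately, the PD wording in 10.3.3 d) (measurable lesions), the target sum in 10.3.2 and the guideline named in 10.3 must be reconciled. Under Section 8.1 PD also triggers removal from therapy, so that wording is for the sponsor to decide and is not proposed here.

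Cost: one sentence and two cross-references. Responders' CT and MRI already go to central review under Section 7.3, so no new imaging is needed. Bone scans are optional and are not on the 7.3 list, so where one was done its result would have to be sent along. The downside is that the observed response rate may be slightly lower.

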## 10.6 Best Response (Solid Tumors)

Two objective status determinations of disease status, by CT or MRI, obtained on two consecutive determinations, separated by at least a 3 week time period, are required to determine the patient’s overall best response. Two objective status determinations of CR before progression are required for best response of CR. Two determinations of PR or better before progression, but not qualifying for a CR, are required for a best response of PR. Two determinations of stable/no response or better before progression, but not qualifying as CR or PR, are required for a best response of stable/no response; if the first objective status is unknown, only one such determination is required. Patients with an objective status of progression on or before the second evaluations (the first evaluation is the first radiographic evaluation after treatment has been administered) will have a best response of progressive disease. Best response is unknown if the patient does not qualify

for a best response of progressive disease and if all objective statuses after the first determination and before progression are unknown.

Table 1: Sequences of objective statuses with corresponding best response.

1st Status	2nd Status	3rd Status	Best Response
Progression			Progressive disease
Stable, PR, CR	Progression		Progressive disease
Unknown	Progression		Progressive disease
Stable	Stable	Progression	Stable
Stable, Unknown	PR, CR	Progression	Stable
Stable, Unknown	Unknown	Progression	Unknown
PR	PR	Progression	PR
PR	CR	Progression	PR
PR, CR	Unknown	Progression	Unknown
CR	CR	Progression	CR
Unknown	Stable	Progression	Stable

Table 2: Overall Response for Patients with Neuroblastoma and Measurable Disease

CT or MRI	MIBG	Bone Scan	Bone Marrow	Catechol	Overall
PD	Any	Any	Any	Any	PD
Any	PD	Any	Any	Any	PD
Any	Any	PD	Any	Any	PD
Any	Any	Any	PD	Any	PD
SD	CR/PR/SD	Non-PD	Non-PD	Any	SD
PR	CR/PR	Non-PD	Non-PD	Any	PR
CR/PR	PR	Non-PD	Non-PD	Any	PR
CR	CR	Non-PD	Non-PD	Elevated	PR
CR	CR	CR	CR	Normal	CR

Table 3: Overall Response Evaluation for Neuroblastoma Patients and MIBG Positive Disease Only

Since patients in Stratum 3 may be enrolled without disease measurable by CT or MRI, any new or newly identified lesion by CT or MRI that occurs during therapy would be considered progressive disease.

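### Progression by size has no minimum absolute rise, so for a single small target lesion a 1-2 mm reading difference can turn an unconfirmed partial response into progressive disease

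*Combined protocol and SAP*

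**What the plan says.** Section 10.3.3 d) defines progression by size as "At least a 20% increase in the sum of the disease measurements for measurable lesions, taking as reference the smallest disease measurement recorded" since treatment began. A new lesion is the other route to PD. No section gives a minimum rise in millimetres.

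Section 10.3.3 b) defines PR as "At least a 30% decrease in the disease measurement" relative to the enrolment measurement. It excludes only new lesions and progression of measurable non-target lesions.

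Section 10.3.1 accepts a lesion that "can be accurately measured in at least one dimension with the longest diameter at least 10 mm", with "CT scan slice thickness no greater than 5 mm". On the number of target lesions it says: "The investigator will identify up to 5 measurable lesions to be followed for response". The sum can therefore rest on a single 10 mm lesion.

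Section 10.6 asks for two determinations of PR or better before a best response of PR is given. It adds that "Patients with an objective status of progression on or before the second evaluations" have a best response of progressive disease, and Table 1 applies this even when the first status was PR or CR. Section 7.3 sends responders and patients with long-term stable disease to central review.

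Section 10.3 opens with "Response and progression will be evaluated in this study using the revised Response Evaluation Criteria in Solid Tumors (RECIST) guideline", version 1.1. The key points it then lists contain no absolute minimum.

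**The concern.** A purely relative threshold shrinks with the tumour. The better the response, the smaller the reference and the fewer millimetres are needed to call progression. For one small lesion the required rise is well below the permitted slice thickness and can plausibly come from reading error alone.

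The timing makes this matter. A PR at the first evaluation is provisional until a second determination. If the second reading is scored as progression, 10.6 makes the best response progressive disease and the patient counts as a non-responder. No section requires a central re-read of a patient the site has scored as progressing. Any such error runs in one direction, lowering the observed response rate, which is the primary endpoint. Each stratum has only 16 evaluable patients.

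**Working it through.** **Plan's own figures.** No stated figure rests on the PD rule. The nearest are the error rates in 9.3 for the endpoint it feeds: type I error 0.079 and power 0.833 with 16 patients. Exact binomial, P(X >= r | n = 16, p):
- r = 5: 0.0791 at p = 0.15 and 0.8334 at p = 0.40, matching 9.3.
- r = 4, the threshold as written: 0.210 and 0.935, which do not match.

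That mismatch is a separate matter; step 4 shows both thresholds.

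**Step 1: millimetres needed for PD.** Rise = 0.20 x smallest sum (10.3.3 d).

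| Smallest sum | Rise scored as PD |
|---|---|
| one lesion, 10 mm | 2.0 mm |
| one lesion, 7 mm (30% response from 10 mm) | 1.4 mm |
| one lesion, 5 mm | 1.0 mm |
| two lesions of 10 mm | 4.0 mm |
| five lesions of 10 mm | 10 mm |

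So 1-2 mm suffices only when the smallest sum is about 5-10 mm.

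**Step 2: when a scan meets both PR and PD.** With baseline B and smallest sum m, PR needs a reading <= 0.70B and PD a reading >= 1.20m. Both are possible only if 1.20m <= 0.70B, that is m <= 0.70/1.20 = 58.3% of B.
- 10, 5, 6 mm: m = 50% of B. The last reading is 40% below baseline (PR) and 20% above m (PD). Nothing in 10.3.3 says which prevails. Scored as progression, Table 1 gives progressive disease on a 1 mm rise.
- 10, 6, 7.2 mm: m = 60% of B. The last reading is 20% above m, but only 28% below baseline. It would not confirm PR at that scan even with an absolute minimum; the label would be SD instead of PD.

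**Step 3: how often reading error alone does this.** Assumptions: one target lesion; true shrinkage constant over both scans; independent normal error on baseline, scan 1 and scan 2; SD 0.75-1.5 mm; PD prevails over PR when both are met; 1,000,000 draws. Among patients with scan 1 <= 0.70 x baseline, count scan 2 >= 1.20 x scan 1, and then only those with scan 2 also <= 0.70 x baseline. The last column is the loss due solely to the PD rule.

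| Shrinkage, baseline | Any PD at scan 2 | PD although still PR by size |
|---|---|---|
| 40%, 10 mm | 18-40% | 11-21% |
| 40%, 15 mm | 7-27% | 5-15% |
| 40%, 20 mm | 2-18% | 2-11% |
| 40%, 30 mm | 0-7% | 0-5% |
| 50%, 10 mm | not needed | 19-28% |
| 50%, 20 mm | not needed | 4-19% |

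With a 5 mm minimum, PD labels of any kind at 40% shrinkage fall to at most 1.3%, which also bounds the last column.

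**Step 4: illustration for a stratum.** Effective rate = 0.40 x (1 - share of true responses lost).

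| Share lost | Effective rate | Power, r = 5 | Power, r = 4 |
|---|---|---|---|
| 0 | 0.40 | 0.833 | 0.935 |
| 5% | 0.38 | 0.789 | 0.912 |
| 10% | 0.36 | 0.739 | 0.883 |

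At the largest 40%-shrinkage loss (21%), an overall loss of 10% would need 0.10/0.21 = 48% of responders to have a single 10 mm target lesion; a loss of 5% would need 0.05/0.21 = 24%. The documents give no such share.

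**The case against.** Several points on the other side stand.

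- A reader might take every PD label after a first PR as a lost response and quote 18-40% at 10 mm. That overstates it: many of those second scans no longer show a 30% decrease and would not confirm PR under any progression rule. Only the last column of step 3 is attributable to the missing minimum.
- A reader might infer a demonstrated loss of power. It is not demonstrated. Neither the reading SD nor the share of patients with one small lesion is in the documents.
- The rule does not cancel confirmed responses: Table 1 keeps PR, PR, progression as PR. Neuroblastoma patients with MIBG-only disease do not use the size rule.
- A reader might say that the printed rule departs from RECIST 1.1, or that RECIST 1.1 already supplies the minimum through 10.3. The guideline's text is not in the documents, so neither can be asserted. What can be said is that 10.3 adopts a guideline, 10.3.3 prints its own definition, and nothing states which governs.
- The 5 mm slice limit is a CT acquisition limit, not a measured reading error, and MRI is also allowed. It is a convenient anchor for a minimum, not proof of the noise level.
- With many target lesions a 5 mm minimum does little. For five 10 mm lesions shrunk 40%, with SD 1.0 mm per lesion, PD at scan 2 is 4.5% without it and 4.4% with it.

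The objection that this is mere abbreviation does not stand. Followed as printed, the rule gives a definite result for 10, 5, 6 mm if progression prevails, and no rule if it does not.

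**Conclusion.** The point holds for patients whose target sum is one small lesion and whose response is not yet confirmed. There, 10.3.3 d) calls progression on 1-2 mm, and in deeper responses it does so on a scan that still meets PR. Under the assumed reading SD and a constant 40% shrinkage, about 11-21% of first-scan PRs at a 10 mm baseline are lost solely through this rule, 5-15% at 15 mm, 2-11% at 20 mm and 0-5% at 30 mm. At 50% shrinkage the loss is 19-28% at 10 mm and 4-19% at 20 mm. The bias is downward and grows with depth of response. Its effect on any stratum's decision cannot be sized from the documents. The change is worth making because it is cheap and removes a known one-sided error.

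**What to change.** For classification of the response endpoint, at site and at central review:

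1. Add to 10.3.3 d) a minimum absolute rise in the sum over the reference, required together with the 20% rise. For example, 5 mm would match the slice-thickness limit in 10.3.1. Keep the new-lesion criterion as it is.
2. State in 10.3 whether RECIST 1.1 by reference or the printed 10.3.3 definition governs where they differ.

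The cost is one clause and one sentence. The downside is small: a few patients with very small lesions would be classed as PD by size one scan later.

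Progression also enters the continuation criteria in 4.1.3 and the removal criteria in 8.1. How the endpoint definition relates to those rules is for the sponsor to reconcile; no treatment rule is proposed here.
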